10.5.2. Study Population

Demographics

Age

- Age will be calculated based on year of birth compared to the date of the screening visit.
- GSK standard IDSL algorithms will be used for calculating age where birth date will be imputed as follows:
 - Any subject with a missing day will have this imputed as day ‘15’.
 - Any subject with a missing date and month will have this imputed as ‘30th June’.
- Birth date will be presented in listings as ‘YYYY’.

Body Mass Index (BMI)

- Calculated as **Weight (kg) / (Height (m))²**

Extent of Exposure

- Number of days of exposure to study drug will be calculated based on the formula:
Duration of Exposure in Days = Treatment Stop Date – (Treatment Start Date) + 1
- Subjects who were randomized but did not report a treatment start date will be categorised as having zero days of exposure.
- The cumulative dose will be based on the formula:
Cumulative Dose = Sum of (Number of Days x Total Daily Dose)
- If there are any treatment breaks during the study, exposure data will be adjusted accordingly.

10.5.3. Safety

ECG Parameters
RR Interval

 IF RR interval (msec) is not provided directly, then RR can be derived as: If QTcB is machine read & QTcF is not provided, then: $RR = \left[\left(\frac{QT}{QTcB} \right)^2 \right] * 1000$ If QTcF is machine read and QTcB is not provided, then: $RR = \left[\left(\frac{QT}{QTcF} \right)^3 \right] * 1000$ If ECGs are manually read, the RR value preceding the measurement QT interval should be a collected value THEN do not derive.
Corrected QT Intervals

 When not entered directly in the eCRF, corrected QT intervals by Bazett's (QTcB) and Fridericia's (QTcF) formulas will be calculated, in msec, depending on the availability of other measurements. IF RR interval (msec) is provided then missing QTcB and/or QTcF will be derived as : $QTcB = \frac{QT}{\sqrt{\frac{RR}{1000}}} \qquad QTcF = \frac{QT}{\sqrt[3]{\frac{RR}{1000}}}$

Adverse Events
AE'S OF Special Interest

 No AE's of special interest have been defined yet. These will not be identified or summarised for SAC.

Laboratory Parameters

 If a laboratory value which is expected to have a numeric value for summary purposes, has a non-detectable level reported in the database, where the numeric value is missing, but typically a character value starting with '<x' or '>x' (or indicated as less than x or greater than x in the comment field) is present, the number of significant digits in the observed values will be used to determine how much to add or subtract in order to impute the corresponding numeric value. 
 Example 1: 2 Significant Digits = '< x' becomes x - 0.01 Example 2: 1 Significant Digit = '> x' becomes x + 0.1 Example 3: 0 Significant Digits = '< x' becomes x - 1

10.5.4. Calculation of Spirometry Screening Parameters

- Derived parameters for spirometry data at screening will be calculated as follows:

Predicted Normal FEV₁

- Predicted Normal FEV₁ will be calculated using the working party of the European Community for Coal and Steel (ECCS) formula [Quanjer, 1993] :

$$\text{Predicted Normal FEV}_1 = b_0 * \text{Height} + b_1 * \text{Age(Yr)} + b_2$$

- The coefficients for male and female subjects are shown in Table 9. Note that no race corrections will be made.

Table 9 Predicted Normal FEV₁ Equation: Coefficients for Male and Female Subjects

	Height (b ₀)	Age (b ₁)	Intercept (b ₂)
Male	0.0430	-0.029	-2.49
Female	0.0395	-0.025	-2.60

% Predicted Normal FEV₁

$$\frac{\% \text{Predicted Normal FEV}_1}{\text{Normal FEV}_1} = \frac{\text{MaxFEV}_1}{\text{Predicted Normal FEV}_1} * 100$$

10.5.5. Pharmacodynamic

Sputum Data
PIP3 Ratio

 PIP3 is the analyte of primary interest for the phospholipid data in sputum, and Peak Area data from the mass spectrometer is the endpoint of interest. However, it is acknowledged that there will be some degree of variability between sputum samples due to differences in cell counts, and therefore it is favoured to first normalise PIP3 Peak Area values by (PIP2 Peak Area + PIP3 Peak Area); prior to analysis. More specifically the parameter of interest is: PIP3 Peak Area proportion (calculated as a proportion of the sum of PIP2 Peak Area and PIP3 Peak Area i.e. PIP3 Peak Area / (PIP2 Peak Area + PIP3 Peak Area)). PIP3 Peak Area, as a proportion of PIP2 Peak Area and PIP3 Peak Area, will be used to calculate the PIP3 Peak Area proportion as follows:

Sputum Data
$PIP3 \text{ Peak Area proportion} = \frac{PIP3 \text{ Peak Area}}{PIP2 \text{ Peak Area} + PIP3 \text{ Peak Area}}$ 
 PIP3 peak area, (PIP3) may be standardised by dividing by a PIP3 standard e.g. ISDPIP3. Similarly, PIP2 peak area (PIP2) may be standardised by dividing by a PIP2 standard e.g. D6PIP2. Multiple standards will be included in the PIP dataset. The unstandardised PIP2 and PIP3 peak areas will be used in the derivation of the PIP3 peak area proportion for the SAC outputs. However, the choice of standards to be used in the analysis may be explored e.g. through comparison of distributions, linear regression post SAC.

10.5.6. Derivation of BAL/ELF Drug Concentration Data

 Urea concentration data will be used to calculate the dilution effect of the lavage which is used to extract the epithelial lining fluid (ELF) from the lung. A correction for dilution will be applied to all BAL fluid drug concentrations for each wash as follows: $ELF \text{ Drug Concentration (pg/mL)} = \frac{BAL \text{ Fluid Drug Concentration (pg/mL)} \times Dilution \text{ Factor}}{Drug \text{ Concentration}}$ 
where
 $Dilution \text{ Factor} = \frac{Plasma \text{ Urea}_{pre-bronch}}{BAL \text{ Urea}}$ 
 Additionally, for each wash, the Volume of ELF in BAL fluid and the Total Drug in BAL fluid will be calculated as follows: $Volume \text{ of ELF in BAL Fluid (mL)} = BAL \text{ Fluid Volume (mL)} / Dilution \text{ Factor}$ $Drug \text{ in BAL Fluid (pg)} = \frac{BAL \text{ Fluid Drug Concentration (pg/mL)} \times BAL \text{ Fluid Volume (mL)}}{Drug \text{ Concentration}}$ 
 Data will then be pooled across all three washes as follows: $Total \text{ Volume of ELF in BAL Fluid (mL)} = \frac{Volume \text{ of ELF in BAL}_{WASH1}}{Drug \text{ Concentration}} + \frac{Volume \text{ of ELF in BAL}_{WASH2}}{Drug \text{ Concentration}} + \frac{Volume \text{ of ELF in BAL}_{WASH3}}{Drug \text{ Concentration}}$ $Total \text{ Drug in BAL Fluid (pg)} = Drug \text{ in BAL}_{WASH1} + Drug \text{ in BAL}_{WASH2} + Drug \text{ in BAL}_{WASH3}$
--

$$\text{Pooled ELF Drug Concentration (pg/mL)} = \frac{\text{Total Drug in BAL Fluid (pg)}}{\text{Total Volume of ELF in BAL Fluid (mL)}}$$

10.5.7. Derivation of BAL Cell Pellet Drug Concentration Data

- Cell pellet samples are diluted in a 1:5 ratio. Concentrations will be corrected for the dilution before the ratio is calculated on an individual subject level between the raw lavage result for wash 2 and the cell pellet concentration:

Derived cell pellet concentration

$$= \frac{\text{cell pellet concentration} \times 5}{\text{wash 2 lavage concentration}} \times \text{derived pooled lavage ELF concentration}$$

- Only the derived concentrations will be included in the listing.

10.6. Appendix 6: Premature Withdrawals & Handling of Missing Data

10.6.1. Premature Withdrawals

Element	Reporting Detail
General	
 • Subject study completion (i.e. as specified in the protocol) was defined as the completion of all phases of the study including the follow up visit. • Withdrawn subjects may be replaced in the study. • All available data from subjects who were withdrawn from the study will be listed and all available planned data will be included in summary tables and figures, unless otherwise specified.

10.6.2. Handling of Missing Data

Element	Reporting Detail
General	
 • Missing data occurs when any requested data is not provided, leading to blank fields on the collection instrument : These data will be indicated by the use of a “blank” in subject listing displays. Unless all data for a specific visit are missing in which case the data is excluded from the table. Answers such as “Not applicable” and “Not evaluable” are not considered to be missing data and should be displayed as such.
Outliers	
 • Any subjects excluded from the summaries and/or statistical analyses will be documented along with the reason for exclusion in the clinical study report.
PK and PD	
 • It is possible that not enough data points will be captured for the sputum at baseline (Part B) and/or at a specific post dose time point for all treatment groups. In such a situation, data should only be listed. No attempt should be made to summarise or statistically analyse the data. • The decision for the summary/statistical analysis of PK and PD data should be made once the study team and statistician have reviewed the totality of available data. • Any values below the Lower Limit of Quantification (LLQ) will be assigned a value of ½ LLQ for display purposes in Figures and for computation of summary statistics. Any values above the Upper Limit of Quantification (ULQ) will be assigned to the ULQ for display purposes in Figures and for computation of summary statistics. If multiple LLQ and /or ULQ values are available per assay (for example if multiple runs with different standard curves are utilised) then the LLQ and/or ULQ value used for the above imputation shall be the minimum of the available LLQs and/or the maximum of the ULQs. Where biomarker concentrations are from an assay of an increased dilution factor the LLQ and ULQ will be multiplied by this factor. • If the number of LLQ (and/or ULQ) values is large for an Individual biomarker then alternative analysis methods such as TOBIT analysis may be required. “Large” is hard to define prospectively and may depend upon the dataset in

Element	Reporting Detail
	
question. Any such methodology will be documented in the statistical contributions to the study report.
 
 • Imputed values will be used in tables and figures, unless the proportion of imputed values at a given time point is large, in which case the summary statistics may not be presented for that time point and/or alternative actions will be taken and documented in the study report. • Where values are imputed, the number of such imputations will be included as a summary statistic in the relevant summary tables.

10.6.2.1. Handling of Missing Dates

PIMS does not capture partial dates, all AEs and con meds will have full dates. Prior medications will have duration and full stop date.

10.6.2.2. Handling of Missing Data for Statistical Analysis

Element	Reporting Detail
PK and PD data	
 • Missing data will not be imputed

10.7. Appendix 7: Values of Potential Clinical Importance

10.7.1. Laboratory Values

Haematology				
Laboratory Parameter	Units	Category	Clinical Concern Range	
			Low Flag (< x)	High Flag (>x)
Hematocrit	Ratio of 1	Male		0.54
		Female		0.54
		Δ from BL	↓0.075	
Hemoglobin	g/L	Male		180
		Female		180
		Δ from BL	↓25	
Lymphocytes	x10 ⁹ /L		0.8	
Neutrophil Count	x10 ⁹ /L		1.5	
Platelet Count	x10 ⁹ /L		100	550
While Blood Cell Count (WBC)	x10 ⁹ /L		3	20

Clinical Chemistry				
Laboratory Parameter	Units	Category	Clinical Concern Range	
			Low Flag (< x)	High Flag (>x)
Albumin	mmol/L		30	
Calcium	mmol/L		2	2.75
Creatinine	mmol/L	Δ from BL		↑ 44.2
Glucose	mmol/L		3	9
Magnesium	mmol/L		0.5	1.23
Phosphorus	mmol/L		0.8	1.6
Potassium	mmol/L		3	5.5
Sodium	mmol/L		130	150
Total CO2	mmol/L		18	32

Liver Function				
Test Analyte	Units	Category	Clinical Concern Range	
ALT/SGPT	U/L	High	≥ 2x ULN	
AST/SGOT	U/L	High	≥ 2x ULN	
AlkPhos	U/L	High	≥ 2x ULN	
T Bilirubin	μmol/L	High	≥ 1.5xULN	
T. Bilirubin + ALT	μmol/L U/L	High	1.5xULN T. Bilirubin + ≥ 2x ULN ALT	

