10.11.4. Safety Tables

Safety : Tables					
No.	Population	IDSL / TST ID / Example Shell	Title	Programming Notes	Deliverable [Priority]
Part A (Single Dose Escalation): Exposure					
2.101	Safety (Part A)	EX1	Summary of Extent of Exposure to Study Treatment (Single Dose)		SAC
Part B (Repeat Dose): Exposure					
2.201	Safety (Part B)	EX1	Summary of Extent of Exposure to Study Treatment (Repeat Dose)		SAC
Part A (Single Dose Escalation): Adverse Events					
2.102	Safety (Part A)	CP_AE1x	Summary of All Adverse Events by System Organ Class (Single Dose)	Include total column.	SAC
2.103	Safety (Part A)	CP_AE1x	Summary of Drug-Related Adverse Events by System Organ Class (Single Dose)	Include total column.	SAC

Safety : Tables					
No.	Population	IDSL / TST ID / Example Shell	Title	Programming Notes	Deliverable [Priority]
2.104	Safety (Part A)	AE15/EMA_AE	Summary of Common ($\geq 5\%$) Non-serious Adverse Events by System Organ Class and Preferred Term (Number of Subjects and Occurrences, Single Dose)		SAC
Part B (Repeat Dose): Adverse Events					
2.202	Safety (Part B)	CP_AE1p	Summary of All Adverse Events by System Organ Class (Repeat Dose)	Include total column.	SAC
2.203	Safety (Part B)	CP_AE1p	Summary of Drug-Related Adverse Events by System Organ Class (Repeat Dose)	Include total column.	SAC
2.204	Safety (Part B)	AE15	Summary of Common ($\geq 5\%$) Non-serious Adverse Events by System Organ Class and Preferred Term (Number of Subjects and Occurrences, Repeat Dose)		SAC
Part A (Single Dose Escalation): Labs					
2.105	Safety (Part A)	LB1	Summary of Chemistry Changes from Baseline by Visit (Single Dose)		SAC
2.106	Safety (Part A)	LB3	Summary of Emergent Chemistry Results by Potential Clinical Importance Criteria (Single Dose)		SAC
2.107	Safety (Part A)	LB1	Summary of Haematology Changes from Baseline by Visit (Single Dose)		SAC
2.108	Safety (Part A)	LB3	Summary of Emergent Chemistry Results by Potential Clinical Importance Criteria (Single Dose)		SAC

Safety : Tables					
No.	Population	IDSL / TST ID / Example Shell	Title	Programming Notes	Deliverable [Priority]
Part B (Repeat Dose): Labs					
2.205	Safety (Part B)	LB1	Summary of Chemistry Changes from Baseline by Visit (Repeat Dose)		SAC
2.206	Safety (Part B)	LB3	Summary of Emergent Chemistry Results by Potential Clinical Importance Criteria (Repeat Dose)		SAC
2.207	Safety (Part B)	LB1	Summary of Haematology Changes from Baseline by Visit (Repeat Dose)		SAC

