2.208	Safety (Part B)	LB3	Summary of Emergent Chemistry Results by Potential Clinical Importance Criteria (Repeat Dose)		SAC
Part A (Single Dose Escalation): ECGs					
2.109	Safety (Part A)	EG2	Summary of Change from Baseline in ECG Values by Visit. (Single Dose)		SAC
2.110	Safety (Part A)	EG1	Summary of Maximum Emergent QTc Values by Category. (Single Dose)		SAC
2.111	Safety (Part A)	EG1	Summary of 12-Lead ECG Findings (Single Dose)		SAC
Part B (Repeat Dose): ECGs					
2.209	Safety (Part B)	EG2	Summary of Change from Baseline in ECG Values by Visit. (Repeat Dose)		SAC
2.210	Safety (Part B)	EG1	Summary of Maximum Emergent QTc Values by Category. (Repeat Dose)		SAC

Safety : Tables					
No.	Population	IDSL / TST ID / Example Shell	Title	Programming Notes	Deliverable [Priority]
2.211	Safety (Part B)	EG1	Summary of 12-Lead ECG Findings (Single Dose)		SAC
Part A (Single Dose Escalation): Vital Signs					
2.112	Safety (Part A)	VS1	Summary of Change from Baseline in Vital Signs by Visit (Single Dose)	Include the Respiration Rate and Tympanic Temperature	SAC
Part B (Repeat Dose): Vital Signs					
2.212	Safety (Part B)	VS1	Summary of Change from Baseline in Vital Signs by Visit (Repeat Dose)	Include the Respiration Rate and Tympanic Temperature	SAC
Part A (Single Dose Escalation): Spirometry					
2.113	Safety (Part A)	PD_PFT1	Summary of Lung Function Data (Single Dose)		SAC
Part B (Repeat Dose): Spirometry					
2.213	Safety (Part B)	PD_PFT1	Summary of Lung Function Data (Repeat Dose)		SAC

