10.11.11. ICH Listings: Part A (Single Dose Escalation)

ICH : Listings					
No.	Population	IDSL / TST ID / Example Shell	Title	Programming Notes	Deliverable [Priority]
Treatment Information					
1.	Screened (Part A)	CP_TA2	Listing of Randomised and Actual Treatments (Single Dose)	To include CENTREID (labelled as INVID), subject no., randomisation no., period, randomised treatment, actual treatment and deviation. Also include PTYN and PTSUBJID from DMDATA.PRVTTRIAL.	SAC
2.	Screened (Part A)	EX4	Listing of Exposure Data (Single Dose)	Dose: extract from actual treatment (if dosing not completed, set to max. possible dose that could have been taken & include footnote). Exclude 'Cumulative Dose' and replace with 'No. Of Inhalations'.	SAC
Disposition					
3.	Screened (Part A)	CP_ES10x	Listing of Reasons for Withdrawal (Single Dose)		SAC
4.	Screened (Part A)	IE4	Listing of Subjects with Inclusion/Exclusion Criteria Deviations (Single Dose)		SAC
5.	Screened (Part A)	DV2	Listing of Protocol Deviations (Single Dose)		SAC
6.	Screened (Part A)	BL2	Listing of Subjects For Whom the Treatment Blind was Broken (Single Dose)		SAC

ICH : Listings					
No.	Population	IDSL / TST ID / Example Shell	Title	Programming Notes	Deliverable [Priority]
Demography					
7.	Screened (Part A)	DM4	Listing of Demographic Characteristics (Single Dose)		SAC
8.	Screened (Part A)	DM10	Listing of Race (Single Dose)		SAC
Concomitant Medications and Adverse Events					
9.	Screened (Part A)	CP_CM4	Listing of Concomitant Medications by Generic Term (Single Dose)		SAC
10.	Screened (Part A)	CP_AE9	Listing of All Adverse Events (Single Dose)		SAC
11.	Screened (Part A)	CP_AE9a	Listing of Serious Adverse Events (Single Dose)		SAC
12.	Screened (Part A)	AE7	Listing of Subject Numbers for Individual Adverse Events (Single Dose)		SAC
13.	Screened (Part A)	CP_AE9	Listing of Adverse Events Leading to Withdrawal from Study (Single Dose)		SAC
Safety Assessments					
14.	Screened (Part A)	CP_LB6	Listing of Clinical Chemistry Abnormalities of Potential Clinical Importance (Single Dose)		SAC
15.	Screened (Part A)	CP_LB6	Listing of All Clinical Chemistry Laboratory Data for Subjects with any Abnormality of Potential Clinical Importance (Single Dose)		SAC
16.	Screened (Part A)	CP_LB6	Listing of Haematology Abnormalities of Potential Clinical Importance (Single Dose)		SAC

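### Creatinine and albumin flagging limits carry a unit that cannot apply, and Tables 2.108 and 2.208 repeat the chemistry titles, so no haematology count table is specified as titled

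*SAP*

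**What the plan says.** Section 10.7.1 (Appendix 7) gives the limits used to flag laboratory values of potential clinical importance. Two rows of the clinical chemistry panel matter here:

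- creatinine, a rise from baseline: "Creatinine mmol/L Δ from BL ↑ 44.2"
- albumin, a low flag: "Albumin mmol/L 30"

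The same appendix sets limits for six haematology parameters: hematocrit, hemoglobin, lymphocytes, neutrophils, platelets and white cells.

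Section 10.11.4 (Appendix 11) lists the tables that use these limits. For Part A the sequence is:

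- the chemistry PCI table: "2.106 Safety (Part A) LB3 Summary of Emergent Chemistry Results by Potential Clinical Importance Criteria (Single Dose"
- Table 2.107: "Summary of Haematology Changes from Baseline by Visit (Single Dose"
- the table after it: "2.108 Safety (Part A) LB3 Summary of Emergent Chemistry Results by Potential Clinical Importance Criteria (Single Dose"

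Part B repeats the pattern. Table 2.207 is "Summary of Haematology Changes from Baseline by Visit (Repeat Dose" and Table 2.208 is "Summary of Emergent Chemistry Results by Potential Clinical Importance Criteria (Repeat Dose", which is also the title of Table 2.206.

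Haematology PCI values do appear in listings. Listing 16, for example, is "Listing of Haematology Abnormalities of Potential Clinical Importance (Single Dose". Listing 17 (Part A) and Listings 39 and 40 (Part B) complete the set.

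**The concern.** Laboratory safety data are a named component of the primary endpoint (sections 1 and 2.2). The limits in section 10.7.1 are operative: they decide who is counted in chemistry Tables 2.106 and 2.206 and who appears in chemistry Listings 14, 15, 37 and 38. A limit paired with an impossible unit, applied as written, flags either nobody or everybody. Listings 15 and 38 show all chemistry data for any subject with a flagged value, so a flag on every albumin result would bring in every subject with an albumin measurement.

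The display list has a different fault. A programmer who follows it literally would produce the chemistry PCI counts twice in each part and no haematology PCI counts by treatment, although haematology limits exist.

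**Working it through.** **Inputs.** From section 10.7.1: creatinine rise above 44.2 mmol/L; albumin below 30 mmol/L. The SAP gives no molar masses, so these are assumed: creatinine 113.12 g/mol (113.12 mg/mmol); albumin 65 to 69 kg/mol (65 to 69 g/mmol).

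**Formula.** Mass concentration = molar concentration × molar mass.

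**Creatinine**

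- As printed: 44.2 mmol/L × 113.12 mg/mmol = 5,000 mg/L = 500 mg/dL.
- With the same number in µmol/L: 0.0442 mmol/L × 113.12 mg/mmol = 5.00 mg/L = 0.50 mg/dL.
- The two readings differ by a factor of 1,000. Only the second is attainable. It is also a round figure in mg/dL, which suggests that the number was intended and the label is wrong.

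**Albumin**

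- As printed: 30 mmol/L × 65 g/mmol = 1,950 g/L; 30 × 69 = 2,070 g/L.
- With the same number in g/L: 30 / 69 = 0.43 mmol/L; 30 / 65 = 0.46 mmol/L.
- The readings differ by a factor of 65 to 69. Every result lies below the printed limit.

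**Could a µ have been lost when the PDF was read?** For creatinine this is unlikely, because the µ in the bilirubin rows and the Δ, ↑ and ≥ signs survive in the same section, but it cannot be excluded. It cannot rescue albumin: 30 µmol/L is 0.030 mmol/L × 65 to 69 g/mmol = 1.95 to 2.07 g/L, so that row would still be wrong.

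**Extent.** The clinical chemistry panel has nine entries: 2 / 9 = 22%.

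**Table titles, side by side**

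| Table | Part | Panel in title | Content |
|---|---|---|---|
| 2.106 | A | Chemistry | PCI counts (shell LB3) |
| 2.107 | A | Haematology | Change from baseline |
| 2.108 | A | Chemistry | PCI counts (shell LB3), same as 2.106 |
| 2.206 | B | Chemistry | PCI counts (shell LB3) |
| 2.207 | B | Haematology | Change from baseline |
| 2.208 | B | Chemistry | PCI counts (shell LB3), same as 2.206 |

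Within each part, the two PCI tables agree in title, population and shell. Of the four LB3 tables, two duplicate the other two, and none is titled for haematology. Tables 2.108 and 2.208 each come directly after a haematology change table, so a title copied from the chemistry row is the natural explanation. That is an inference from the order of the tables.

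**The case against.** The strongest reply is that these are proofreading slips with little practical effect. Nothing in the SAP tells anyone to convert results to mmol/L before flagging. If the bare numbers are applied to values in the laboratory's own units, the flags may work as intended. The creatinine label is also less certain than albumin, because the surviving µ signs are in a different panel of the section.

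On the titles, overview Table 3 in section 7.1.3 marks no PCI count table for either panel. What it does promise for haematology, a change summary and two PCI listings, is delivered in both parts. Section 10.5.1 mentions PCI summary tables only in general terms. Two identical tables would serve no purpose, so most readers would guess that haematology was meant.

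Much of this stands. The effect on the flags is conditional on a literal reading, the effect is descriptive only, and the haematology intent is inferred. It does not remove the point. Flags that work only if the printed unit is ignored depart from the written plan, and the SAP is what programming and quality control work from. A lost character cannot explain the albumin row. The duplicated titles are plain in the display list, and an output that must be guessed from its position has not been specified.

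**Conclusion.** The point holds and is minor. Two of nine clinical chemistry limits are printed with a unit that cannot apply: creatinine is too large by a factor of 1,000 relative to the workable reading, and albumin by a factor of 65 to 69. Applied literally, the first would flag no one and the second everyone with a result. The albumin error is certain; the creatinine error is very probable, with a small reservation about text extraction. The factor for albumin rests on the assumed molar mass, but the conclusion does not depend on its exact value.

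Two of the four PCI count tables duplicate the other two, leaving none for haematology as titled. Individual haematology values remain available in four listings. No estimate, confidence interval or test in the plan changes.

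**What to change.** In section 10.7.1, keep both limits and reconcile the unit labels with the units in which the laboratory reports creatinine and albumin. The printed numbers are workable as µmol/L and g/L respectively, but the sponsor should confirm this against the laboratory's specification.

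In section 10.11.4, replace Chemistry with Haematology in the titles of Tables 2.108 and 2.208, after confirming that haematology was intended.

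The cost is two unit labels, two titles and one check with the laboratory, with no change to any analysis.
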